### **3.3 Inclusion Criteria**

- a. between 21-70 years old
- b. presents with symptomatic haemorrhoids as evident from clinical assessment
- c. never had any haemorrhoid-related operations performed on them before
- d. fit for general anaesthesia
- e. able to give informed consent
- f. willing to be randomized
- g. willing to fill in post-operative questionnaires and be compliant to follow up

### **3.4 Exclusion Criteria**

- a. Are pregnant
- b. Are prisoners
- c. Intellectually, mentally or emotionally deemed not able to provide an informed consent and/or are unable to fill up the post-procedure questionnaires/VAS score
- d. Have had previous haemorrhoid procedural treatment before (except Rubber Band Ligation)
- e. Declined endoscopic evaluation
- f. Are on anti-platelets and/or anti-coagulation
- g. Have history of thrombophilia
- h. Are on steroids
- i. Have haemorrhoids which are incidentally found on endoscopy/clinical examination but are asymptomatic from it

### **3.5 Subject Replacement**

Subjects who drop out are accounted for in the sample size calculation and will not be replaced.

## **4 STUDY DESIGN**

This is a single-center, double-blind randomized controlled trial to be conducted in Sengkang General Hospital.

All patients presenting to the clinic or admitted for symptomatic haemorrhoids would be assessed for recruitment.

Figure 1 shows the enrolment process of the study population in the trial. Patients will be seen in the

clinic or in the wards for symptomatic haemorrhoids. All these patients would be approached and be introduced to this study but not recruited yet.

Patients older than 40 years-old with no recent colonoscopy (within 5 years) would need to have a colonoscopic evaluation of the colon after the index admission/clinic visit.

Those younger than 40 would be advised to have a rigid sigmoidoscopy on the day of the operation during the examination under anaesthesia. Only after agreement to the above, the patient would be recruited into the study. They would then be educated on the peri-operative questionnaire separately by a research administrator after recruitment into the trial.

The peri-operative package is split into pre- and post-operative components and will include basic demographics, baseline haemorrhoid-specific QoL questionnaires, VAS scales for POD0-10 and details of the intraoperative procedure and intraoperative description of the haemorrhoids.

Patients who fit the inclusion and exclusion criteria would be recruited into the study. We will perform a 1:1, block-of-4 randomization using a computer-generated programme performed by an independent research administrator who is not part of the surgical team.

They will be allocated only after they are examined under anaesthesia. Allocation is provided in a concealed opaque envelope that is provided by the research administrator on the day of the operation. Thus, the patient is blinded to the procedure. There will also be no cross-over from one study arm to another.

Potential Difficulties and Alternative Approaches to achieve the aims:

Difficulty of recruitment of patients into the trial may be potentially present especially for a procedure that is new in Singapore. Patient counselling and explanation of the procedure would be important and offering a short video clip of the procedure may be helpful. The procedurists/co-investigators of the study team would also be trained by a regional practitioner of the technique before the initiation of the trial to ensure proficiency for reassurance.

Accurately assessing the pain scores and QoL measures may be subjective and laden with the potential of recall and interviewer biases. In order to mitigate this, the patients will be instructed on the proper way of performing a VAS assessment of their pain before the procedure when they are not bothered by any sort of discomfort from the procedure. In addition, our research administrators would be briefed and trained to conduct an objective QoL assessment prior to the initiation of the trial.

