### **3.2 Criteria for Recruitment and Recruitment Process**

Patients who are seen in the specialist outpatient clinics (SOC) or who are admitted for haemorrhoid-related symptoms/complications will be evaluated by one of the PI/co-PIs. All of them would need to have the usual clinical and endoscopic assessment of the colon to ascertain that the haemorrhoids are the only cause of their symptoms. They also should not have previous operation for haemorrhoids, excluding rubber band ligations. Only after the above would they be eligible for recruitment into the study.

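### No pre-operative VAS is listed, so the primary pain comparison cannot be adjusted for existing pain on its own scale: a minor, cheaply fixed loss of precision

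*Protocol*

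**What the plan says.** **Who is enrolled.** Protocol section 3.2 takes clinic patients and those "who are admitted for haemorrhoid-related symptoms/complications will be evaluated by one of the PI/co-PIs". Section 4 repeats this: "All patients presenting to the clinic or admitted for symptomatic haemorrhoids would be assessed for recruitment". Section 3.4 excludes people whose haemorrhoids cause no symptoms. Section 1.1 gives bleeding and anal discomfort as the usual presentations.

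**What is measured.** The primary objective (section 2.2) is daily VAS over the first 10 days after surgery. Section 4 describes the package: "The peri-operative package is split into pre- and post-operative components and will include basic demographics, baseline haemorrhoid-specific QoL questionnaires", followed by "VAS scales for POD0-10 and details of the intraoperative procedure and intraoperative description of the haemorrhoids". The word baseline is attached to QoL, a secondary outcome, and not to VAS. Later in section 4, patients are to be "instructed on the proper way of performing a VAS assessment of their pain before the procedure". That is instruction; no recorded score is mentioned.

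**How it is allocated and compared.** Section 4.1 gives 1:1 allocation in blocks of 4, from an opaque envelope, after examination under anaesthesia, and names no stratification factor. Section 9.2(a) compares continuous variables by the Mann-Whitney U test, without covariates.

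**The concern.** Patients who come in bleeding and patients who come in with pain may start from different places on the VAS, and admitted patients may differ from clinic patients. Some of the spread in post-operative VAS could then come from pain present before the operation. A pre-operative score on the same scale is the natural covariate for removing that part of the spread and for correcting a chance difference between arms.

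This is a matter for the protocol and not only for an analysis plan. An analysis plan can choose covariates, but it cannot recover a score that was never taken. At stake are some precision on the primary outcome and a direct check that the arms began with similar pain.

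**Working it through.** **1. The plan's own figure.** Inputs from section 9.1: 50% versus 25% with VAS above 7.5, power 80%, alpha 5% (two-sided assumed), 10% loss. With pooled variance and no continuity correction, and mean proportion 0.375:

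- n = [1.960 × √(2 × 0.375 × 0.625) + 0.842 × √(0.5 × 0.5 + 0.25 × 0.75)]² / 0.25²
- = (1.342 + 0.557)² / 0.0625 = 57.7, so 58 per arm
- 58 × 1.10 = 63.8, so 64 per arm, as stated.

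This reproduces the plan. A baseline VAS plays no part in it, so the figure neither supports nor refutes the concern.

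**2. Does existing pain bias the comparison?** Simulation under no treatment effect: 58 per arm, VAS drawn from a normal distribution (mean 5.5, SD 2, clipped to 0–10), a share of patients given 2 extra points whichever arm they are in, 1:1 random allocation (blocks of 4 not modelled), Mann-Whitney test at 5%, 4,000 repeats. These settings are assumptions.

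| Share with 2 extra points | Type I error |
|---|---|
| 10% | 5.1% |
| 30% | 5.0% |
| 50% | 5.2% |

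The simulation error is about √(0.05 × 0.95 / 4000) = 0.3 percentage points, so all three agree with 5%. There is no bias.

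**3. What could adjustment gain?** Let r be the correlation between pre- and post-operative VAS. The documents give no value, so 0.3 to 0.5 is assumed. For a linear covariate model of continuous VAS:

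| r | Variance removed, r² | Standard error multiplied by √(1 − r²) |
|---|---|---|
| 0.3 | 0.09 (9%) | √0.91 = 0.95 |
| 0.5 | 0.25 (25%) | √0.75 = 0.87 |

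Confidence intervals would be about 5% to 13% narrower. At r = 0.2 the variance removed is only 4%.

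**4. How large is chance imbalance?** With 58 per arm, the difference in mean pre-operative VAS has a standard deviation of √(2/58) = 0.19 baseline SDs. A one-SD imbalance moves the post-operative difference by r × 0.19, which is 0.06 to 0.09 outcome SDs. The unadjusted standard error already allows for this. It is the same gain as in step 3 seen from another side, and should not be added to it.

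**The case against.** The strongest reply is that nothing here threatens validity. That stands. A reader might infer that disease pain contaminates the primary outcome and cannot be taken out. The documents do not support this: allocation follows examination under anaesthesia and balances prior pain in expectation, and the baseline haemorrhoid QoL questionnaire is a partial covariate.

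Nor does the text say that admitted patients have surgery during that admission or are still in pain at operation. Section 4 introduces the study before recruitment and, for those over 40 without a recent colonoscopy, places colonoscopy after the index admission or visit. Some may well have settled by then.

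Three further inferences go too far:

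- **A larger effective sample.** 58 / (1 − r²) gives 64 to 77 per arm, but that formula is for a linear model of a continuous outcome. The 58 comes from a comparison of proportions, so the figures do not carry over.
- **A shift in the result.** If 25% of patients were admitted cases scoring 2 to 3 points higher after surgery, the imbalance in their share has SD √(2 × 0.25 × 0.75 / 58) = 0.080. At 1.96 SD this moves the arm difference by 0.3 to 0.5 points. That is a tail event on assumed inputs (0.16 to 0.24 points at one SD), and the p-value already allows for it.
- **A loss of power.** In an extreme case where 10% or 20% of patients exceed 7.5 from disease pain in either arm, power at 58 per arm falls from 80% to 69% or 58%. The documents give no such share, and the 50% and 25% planning rates may already describe a mixed population.

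Two more points stand. Appendix 2, the questionnaire package, is attached separately and not shown, and its pre-operative part may hold a VAS. Route of entry could also be available from the source records named in section 14, so a description by route does not depend on a baseline VAS.

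What the reply does not remove is that section 4 itemises the package, labels QoL as baseline and gives VAS only from POD0. POD0 is the day of surgery and cannot be assumed to be a score taken before it.

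**Conclusion.** The point holds as a minor one. As written, the protocol lists no baseline for its own primary outcome, although it enrols symptomatic patients by two routes and already teaches each of them the scale before surgery. The cost is some precision, and a chance imbalance in existing pain that can be adjusted only through a proxy. The cost is not bias.

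The gain from correction is unknown. The 9% to 25% of variance rests on an assumed correlation of 0.3 to 0.5 and applies to a linear analysis of continuous VAS, not to the proportion above 7.5. The conclusion also depends on Appendix 2: if a pre-operative VAS is there, only the description in section 4 needs correcting.

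**What to change.** In section 4, add one VAS to the pre-operative part of the package, taken on the day of surgery before the envelope is opened. Because allocation follows examination under anaesthesia, any score the patient gives before anaesthesia meets this condition. If Appendix 2 already contains the score, say so in section 4.

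Record route of entry (clinic or admitted) as a check box. In section 9.2, add an analysis of VAS adjusted for the pre-operative score, reported alongside the Mann-Whitney test. Any results by route of entry should be descriptive only: with an assumed 25% admitted there would be about 0.25 × 58 = 14 to 15 such patients per arm.

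The cost is one VAS line, one check box and one covariate model. Treatment, eligibility and sample size are unchanged. The change has to be made before enrolment to cover every patient, since the score cannot be recovered afterwards.

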### **2.2 Primary Objectives**

Daily visual analogue pain scale (VAS) in the first 10 days after surgery.

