#### **4.1 Randomisation and Blinding**

Patients who fit the inclusion and exclusion criteria would be recruited into the study. We will perform a 1:1, block-of-4 randomisation using a computer-generated programme performed by an independent research administrator who is not part of the surgical team.

They will be allocated only after they are examined under anaesthesia. Allocation is provided in a concealed opaque enveloped that is provided by the research administrator on the day of the operation. Thus, the patient is blinded to the procedure. There will also be no cross-over from one study arm to another.

An independent research administrator, not part of the randomisation process, will also contact the patient 3 months and 1 year after the procedure as mentioned above.

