## 4.3 Study Visits and Procedures

### 4.3.1 Screening Visits and Procedures

Patients will be seen in the clinic or in the wards for symptomatic haemorrhoids. All these patients would be approached and be introduced to this study but not recruited yet.

Figure 2 illustrates the visits commitment throughout the study process. After the completion of surgery, patients typically would already have a follow up appointment at 4-6 weeks after the procedure. The clinician will assess the patients progress and examining them for any complications. If their recovery is smooth, most of these patients would be discharged from follow up. During the same setting, the research administrators would collect back the peri-operative package from the patient.

Research administrators would then conduct a phone interview with the patients at 3-month and 1-year after surgery to perform the QoL survey and also looking out for late-onset complications and recurrence of symptoms. If present, they will be offered to have an appointment booked with their primary surgeon. Patients would be informed of the allocation at the clinic review at 4-6 weeks. As none of the visits are outside of normal practice, no remuneration is required.

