## **6.5 Blinding**

Patients will be allocated only after they are examined under anaesthesia. Allocation is provided in a concealed opaque enveloped that is provided by the research administrator on the day of the operation. Thus, the patient is blinded to the procedure. There will also be no cross-over from one study arm to another.

An independent research administrator would conduct a phone interview with the patients at 3-month and 1-year after surgery to perform the QoL survey and also looking out for late-onset complications and recurrence of symptoms. If present, they will be offered to have an appointment booked with their primary surgeon. Patients would be informed of the allocation at the clinic review at 4-6 weeks.

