## **8.2 Data Entry and Storage**

Data will be entered into a data collection sheet by the study team or on the peri-operative package by the patient. All these data will be scanned in and images stored in a dedicated encrypted external hard-drive for archiving purposes. Hard-copy forms will be stored in a ring-file that is kept under lock-and-key by the PI. The data on the 2 data collection forms will be separately entered into an password-protected excel document, not having any patient identifiers, and stored in the dedicated encrypted hard-drive in a separate folder for the purposes of data analysis.

Only the study administrators and study co-investigators will have access rights for data entry and analysis though the PI.

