## **9 SAMPLE SIZE AND STATISTICAL METHODS**

### **9.1 Determination of Sample Size**

Based on previous studies, as well as unpublished results from surgeons who have performed LAH around the South East Asian region, we are expecting 50% of the patients in the COH arm to have a VAS score of more than 7.5. We expect to see 25% patients in the LAH arm having a VAS score of more than 7.5.

With a power of 80%, chance of type 1 error (alpha) less than 5% and accounting for 10% of loss to follow up rate, the sample size required for the study to be adequate powered is having 64 patients in each arm (N=128).

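### The protocol lists operative details in the same patient-held package as the POD0-10 pain scales and states no safeguard, leaving open a route to unblinding during primary-outcome scoring

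*Protocol*

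**What the plan says.** Five parts of the protocol bear on this.

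- **Outcome.** Section 2.2 gives the primary objective as "Daily visual analogue pain scale (VAS) in the first 10 days after surgery".
- **Package contents.** Section 4 says "The peri-operative package is split into pre- and post-operative components". It then lists what the package holds: demographics, the baseline quality-of-life questionnaires, and "VAS scales for POD0-10 and details of the intraoperative procedure and intraoperative description of the haemorrhoids".
- **Who completes it.** Section 8.2 says "Data will be entered into a data collection sheet by the study team or on the peri-operative package by the patient". It goes on to refer to two data collection forms.
- **Who holds it.** Section 4.3.1 says that at the 4-6 week clinic review "the research administrators would collect back the peri-operative package from the patient".
- **Blinding.** Section 4.1 explains that the envelope is used only after examination under anaesthesia and concludes "Thus, the patient is blinded to the procedure". Section 6.5 adds "Patients would be informed of the allocation at the clinic review at 4-6 weeks", and Section 4.3.1 says the same.

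The package itself is Appendix 2, attached separately and not available here.

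**The concern.** The outcome is subjective and self-reported, so it depends on the patient not knowing which operation was done. For the POD0-10 scores, blinding of the patient is the only protection the protocol describes. Section 4 calls the trial double-blind, but the independent administrator in Sections 4.1 and 6.5 is assigned to the 3-month and 1-year calls, well after pain scoring has ended.

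If the form in which pain is scored also carries a description of the operation, a patient could read it while scoring. Section 4 foresees counselling about the new procedure, possibly with a video, so such a description could be recognised. Section 2.4.2 presents the laser procedure as possibly less painful. An expectation effect, if there were one, would therefore probably favour LAH. Scores given with knowledge of the allocation cannot be repaired in the analysis.

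**Working it through.** The point contains no figure to recompute, so the check sets the sections side by side.

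**1. Does the scoring window fall inside the blinded period?** Scoring ends on POD10. Disclosure is at 4-6 weeks, that is day 28 to day 42. The planned disclosure therefore comes 28 − 10 = 18 to 42 − 10 = 32 days after the last score. The intended timeline protects the outcome, provided nothing reveals the allocation earlier.

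**2. Where is the package during scoring?** The patient writes on it (8.2) and it is recovered from the patient at 4-6 weeks (4.3.1). At least the part with the VAS scales is with the patient throughout POD0-10.

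**3. Where are the operative details?** Section 4 assigns them to the package, in the same list item as the VAS scales. No section assigns them to the study team's sheet.

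**4. Does the pre-/post-operative split separate them from the VAS scales?** The protocol does not say which component holds them. Allocation happens only once the patient is anaesthetised, so details of the allocated procedure cannot be filled in before surgery. With two components, the natural place is the post-operative one, where the POD0-10 scales also belong. This is an inference from timing, not a statement in the protocol.

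**5. Is a safeguard stated?** The mechanism in Sections 4, 4.1 and 6.5 is the envelope used under anaesthesia. It keeps the patient unaware up to the end of surgery. No section says that the operative part is detached, sealed, coded or kept by staff afterwards. The mitigation Section 4 offers for subjective scoring is VAS instruction and interviewer training, which does not address knowledge of the allocation.

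| Question | Literal reading of Sections 4, 4.3.1, 8.2 | Sections 4.1, 6.5 |
|---|---|---|
| Can the patient see operative details before 4-6 weeks? | Not excluded: they are in a package the patient holds | Must not be possible |

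**6. Does this touch the sample size?** No. With 50% against 25% above VAS 7.5 (Section 9.1), two-sided alpha 0.05 (sidedness is not stated, so this is an assumption) and 80% power:

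n = [1.96·√(2·0.375·0.625) + 0.842·√(0.5·0.5 + 0.25·0.75)]² / 0.25² ≈ 57.7, so 58 per arm.

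Allowing for 10% loss gives 58 × 1.1 = 63.8, so 64, or 58 / 0.9 = 64.4, so 65. The stated 64 per arm reproduces. The issue here is possible bias, which this arithmetic does not measure.

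**The case against.** The strongest case on the other side is that Section 4 is a loosely worded inventory, not a procedure. An anaesthetised patient cannot record operative findings. Section 8.2 divides the work between a sheet completed by the study team and a package completed by the patient, so the operative details may already sit on the staff sheet. Appendix 2 is titled as a post-procedure questionnaire, which fits a patient form better than an operative record. The content of the operative details is undefined, and nothing says that a page naming the technique goes home. Collecting the package back does not prove that every component was with the patient. The intent to blind is clear and stated repeatedly.

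Much of this stands. A reader might infer that every patient would be unblinded, and from the day of surgery. The document does not support that: it never says the patient is given or shown the operative details, and the package cannot be inspected.

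The objection does not remove the conflict. Section 4 expressly puts the operative details in the package, no section puts them on the staff sheet, and no section says they are kept from the patient. The existence of the staff sheet shows that the conflict is easy to resolve, not that it has been resolved.

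**Conclusion.** The point holds as an unresolved contradiction. Taken literally, the description of the package in Sections 4, 4.3.1 and 8.2 leaves a route by which a patient could learn the operation while scoring the primary outcome, against the blinding promised in Sections 4.1, 4.3.1 and 6.5. No safeguard is stated.

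Actual unblinding is not established. How many patients could be affected depends on the layout and handling of Appendix 2. No bias in VAS points, or in the proportion above 7.5, can be derived from the document. The likely direction, in favour of LAH, is a judgement based on how the protocol presents the procedure. The conclusion assumes that the package in Section 4 is the one meant in Sections 4.3.1 and 8.2, which the shared name supports.

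It is worth correcting because the outcome is self-reported, the scores cannot be repaired afterwards, and the correction is nearly free.

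**What to change.** In Section 4, take the operative details and the intraoperative description out of the patient-held package. In Section 8.2, and where its text is repeated in Sections 12.2 and 14, state that they are recorded only on the study team's data collection sheet. Add one sentence to Section 4.1 or 6.5 saying that the patient-held VAS component contains nothing that reveals the allocation before disclosure at the 4-6 week review. Check Appendix 2 against this before packages are issued.

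The cost is a few sentences and, if Appendix 2 does contain an operative page, moving that page to a form that already exists. No patients, visits, staff or analyses are added, and the sample size does not change.
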